8.7.5. Specified Protein Research

Blood samples will be collected for potential exploratory biomarker assessment in serum associated with response as specified in the SoA.

8.7.6. Specified Metabolomic Research

Specified metabolomic research is not included in this study.

8.7.7. Retained Research Samples for Biomarkers

These Retained Research Samples will be collected in this study:

- blood for Prep B2.5 optimized for serum
- blood for Prep R1 optimized for serum

Retained Research Samples will be collected as local regulations and IRBs/ECs allow according to the SoA.

Retained Research Samples will be collected as local regulations and IRBs/ECs allow according to the SoA.

Retained Research Samples may be used for research related to the study intervention(s) PAH. Genes and other analytes (eg, proteins, RNA, nondrug metabolites) may be studied using the retained samples.

See Section 10.5 Appendix 5 for information regarding genetic research. Details on processes for collection and shipment of these samples can be found in the laboratory manual.

8.8. Immunogenicity Assessments

Blood samples will be collected for determination of immunogenicity as specified in the SoA. Instructions for the collection and handling of biological samples will be provided in the laboratory manual or by the sponsor. The actual date and time (24-hour clock time) of each sample will be recorded.

Samples will be analyzed using a validated analytical method in compliance with applicable SOPs.

Samples collected for determination of immunogenicity may also be used for additional characterization of the immune response and/or evaluation of the bioanalytical method, or for other internal exploratory purposes. These data will be used for internal exploratory purposes and may not be reported in the CSR.

The immunogenicity samples must be processed and shipped as indicated in the instructions provided to the investigator site to maintain sample integrity. Any deviations from the immunogenicity sample handling procedure (eg, sample collection and processing steps, interim storage, or shipping conditions), including any actions taken, must be documented and reported to the sponsor. On a case-by-case basis, the sponsor may make a determination as to whether sample integrity has been compromised.

Immunogenicity information that would unblind the study will not be reported to investigator sites or blinded personnel until the study has been unblinded.

Any changes in the timing or addition of time points for any planned study assessments must be documented and approved by the relevant study team member and then archived in the

sponsor and site study files but will not constitute a protocol amendment. The IRB/EC will be informed of any safety issues that require alteration of the safety monitoring scheme or amendment of the ICD.

8.9. Health Economics

Health economics/medical resource utilization and health economics parameters are not evaluated in this study.

9. STATISTICAL CONSIDERATIONS

Detailed methodology for summary and statistical analyses of the data collected in this study is outlined here and further detailed in the SAP, which will be maintained by the sponsor. The SAP may modify what is outlined in the protocol where appropriate; however, any major modifications of the primary endpoint definitions or their analyses will also be reflected in a protocol amendment.

9.1. Statistical Hypotheses

9.1.1. Part A

No formal statistical hypothesis testing will be performed for part A of this study.

9.1.2. Part B

NT-proBNP Endpoint

Null hypothesis for NT-proBNP for Part B of this study is that the mean observed NTproBNP change from baseline at 24 weeks in PAH patients on PF-07868489 is no different than the mean observed NT-proBNP change from baseline at 24 weeks in PAH patients on placebo. The alternative hypothesis is that mean NT-proBNP levels decline from baseline at 24 weeks for PAH patients on PF-07868489 relative to PAH patients on placebo.

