9.3.2.2. Change in NT-proBNP

9.3.2.2.1. Main Analysis

- Estimand strategy: Hypothetical (Section 9.1.1).
- Analysis set: PD-Biomarker Analysis (Section 9.2).
- Analysis methodology: Change from baseline relative to placebo will be analyzed using a linear mixed model including data from Weeks 4, 8, 12, 16, 20 and 24 with treatment and time and fixed effect (Section 9.3.1) with subject (and/or time) as a random effect and an unstructured covariance matrix for random effects ie, a random intercepts and slopes model. If the above model does not converge, random intercepts and slope models with different covariance matrix specifications (eg, compound symmetry) will be tried.
- Intercurrent events and missing data: Data after study drug discontinuation and rescue will be excluded; intermediate missing values will not be imputed.
- The sample size, mean, standard deviation, median, minimum, and maximum at the baseline and postbaseline visits for observed NT-proBNP and change from baseline will be presented for treatment and placebo.
- The least-squares (LS) means, the 95% confidence interval for the LS means, the difference between the LS means for each treatment arm, and the corresponding 95% confidence interval will be presented for change from baseline in NT-proBNP for all post-baseline visits.

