9.5. Sample Size Determination

Part A

No formal sample size calculations were performed for part A. Cohort size of approximately 4 to 8 participants have been chosen to ensure appropriate sample size to provide adequate safety, tolerability and PK information at each dose level and to provide a placebo comparison group, while minimizing exposure to humans of a new biologic entity. A sufficient number of participants will be screened to achieve 4 participants to be randomized in Cohort 1. For Cohorts 2 and 3, 6 participants and for Cohorts 4, 5 and 6, 8 participants will be randomized. Cohorts 7 and 8 will only screen and randomize 5 Japanese and Chinese participants respectively. For the first two cohorts in Part A (Cohorts 1 and 2) participants will be randomly assigned to PF-07868489 or placebo in a ratio of 1:1 and randomization ratio, 2:1 for Cohorts 3 and 4, 3:1 for Cohorts 4, 5 and 6; 4:1 in the Japanese (Cohort 7) and Chinese (Cohort 8) cohort. A total of approximately 36 participants will be randomized (without any optional cohorts) or up to 54 (with 3 optional cohorts) will be enrolled into the study.

Part B

Sample size determination for part B is based on the primary endpoint of change in NTproBNP, of PF-07868489 vs. placebo which will be evaluated at 24 weeks (Section 9.1.2). Assuming an inter-subject correlation of 0.85, 15% of patients drop out for non-study reasons and a type 1 error rate of .05, a total of 36 PAH patients randomized 1:1 to either PF-07868489 or placebo (to obtain 15 evaluable patients per arm) provides greater than 90% power to reject the null hypothesis – that is, the mean observed NT-proBNP change from baseline at 24 weeks in PAH patients on PF-07868489 is no different than the mean observed NT-proBNP change from baseline at 24 weeks in PAH patients on placebo – when the true difference is that the post-baseline decline of NT-proBNP at least 45% greater than placebo.

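### The primary NT-proBNP endpoint is powered on a relative effect but tested as a plain difference in mean change, and no SD is given, so the stated power above 90% cannot be verified for the written analysis

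*Protocol*

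**What the plan says.** **Sample size (Protocol 9.5, Part B).** The design is "a total of 36 PAH patients randomized 1:1 to either PF-07868489 or placebo". This is meant to leave 15 evaluable in each arm and to give power above 90%. The other inputs are "Assuming an inter-subject correlation of 0.85" and "15% of patients drop out for non-study reasons and a type 1 error rate of .05". The effect to be detected is relative: "when the true difference is that the post-baseline decline of NT-proBNP at least 45% greater than placebo". No concentration difference, SD, CV or baseline level is given, and the text does not say whether the 0.05 is one- or two-sided.

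**Hypothesis (9.1.2).** The null is that "the mean observed NTproBNP change from baseline at 24 weeks in PAH patients on PF-07868489 is no different than" the corresponding mean on placebo. The alternative is directional and also stated in levels: "The alternative hypothesis is that mean NT-proBNP levels decline from baseline at 24 weeks for PAH patients on PF-07868489 relative to PAH patients on placebo".

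**Estimand (synopsis, 3.2, 9.1.3.1).** E1 is the treatment difference in mean change from baseline in NT-proBNP.

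**Primary model (9.3.2.2.1).** "Change from baseline relative to placebo will be analyzed using a linear mixed model", using six post-baseline visits from Week 4 to Week 24. No transformation and no baseline covariate is named. Results are LS means and their differences for change from baseline. Descriptive summaries are the mean, SD, median and range of observed values and changes.

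**Room left to the SAP.** The opening of section 9 lets the SAP modify the plan, but says that major modifications to primary endpoint definitions or their analyses will also appear in a protocol amendment.

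**The concern.** A percentage effect and a difference in mean change are different quantities. If treatment lowers NT-proBNP by a given fraction, each participant's absolute fall is proportional to that participant's own baseline. With right-skewed values, the untransformed changes are then skewed, their variance depends on baseline and on treatment arm, and a few high-baseline participants carry much of the mean. With about 15 evaluable per arm, that matters.

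A 45% effect can be turned into a difference in mean change only with a baseline level and an SD, and 9.5 supplies neither. The power statement therefore does not describe the test that 9.1.2, E1 and 9.3.2.2.1 set out. This is the only endpoint with a power calculation. A true effect of the planned size could be missed, or the estimate could rest on a few participants. If the scale were settled only after data had been seen, the primary result would be open to challenge.

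The correlation is also misnamed. Different participants are independent, so a correlation between subjects cannot reduce the variance of change. The 0.85 can enter the calculation only as a within-subject correlation between visits.

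**Working it through.** **1. The plan's sample size reproduces.** 15/(1 − 0.15) = 17.6, so 18 per arm and 36 in total.

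**2. The plan's power cannot be reproduced.** It needs an SD and none is given. What can be done is to solve for the SD that would be required, then compare scales over a range.

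*Inputs from 9.5:* 15 evaluable per arm, alpha 0.05, correlation 0.85, 45% effect. *Assumptions of mine:* two-sided test; 45% read as a Week 24 ratio of 0.55 to placebo; 0.85 read as the baseline-to-Week 24 correlation on the log scale; log-normal values; flat placebo arm; log-SD (σ) from 0.6 to 1.2.

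**3. Log scale.** δ = |ln 0.55| = 0.598. SD of log change = σ√(2(1 − 0.85)) = 0.548σ. With 15 per arm (28 df, noncentral t), 90% power needs δ/SD = 1.226, so:

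- maximum SD of log change = 0.598/1.226 = 0.487
- maximum σ = 0.487/0.548 = 0.89

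The normal approximation gives 0.92. The claimed power is therefore attainable on the log scale if σ is no more than about 0.9.

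**4. Same effect tested as untransformed change.** Log-normal baseline and Week 24 values were simulated (at least 20,000 trials per σ), with a two-sided t-test on Week 24 change. The last column adds an untransformed baseline covariate, which 9.3.2.2.1 does not name.

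| Assumed log-SD | Log change | Untransformed change | Untransformed, with baseline covariate |
|---|---|---|---|
| 0.6 | 99.8% | 89% | 98% |
| 0.8 | 95% | 62% | 82% |
| 0.89 | 90% | 50% | 70% |
| 1.0 | 82% | 39% | 57% |
| 1.2 | 67% | 24% | 36% |

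Untransformed change reaches 90% only when σ is about 0.59 or less (94% at 0.55, 97% at 0.50).

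**5. How far the untransformed figures move under other choices.**

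- One-sided 0.05: 94% at σ = 0.6, 90% at 0.65, 65% at 0.89.
- Mean of six exchangeable visits against baseline with a constant effect, a rough bound on what repeated visits could add: about 95%, 77%, 65% and 54% at σ = 0.6, 0.8, 0.89 and 1.0.
- Placebo worsening by 20%: 96% at σ = 0.6, 87% at 0.7.

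**6. Another reading of the 45%.** Taken as percentage points of percent change, 90% two-sided power by the normal approximation needs a standardised effect of √(2/15) × (1.960 + 1.282) = 1.184. The SD could then be at most 45/1.184 = 38 points. That SD is not stated either.

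**7. Influence of a few participants.** At σ between 0.8 and 1.0, the three highest-baseline participants of 15 supply a median of 45% to 51% of an arm's expected absolute fall.

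**The case against.** A reader might infer that the primary analysis fails to deliver 90% power. The documents do not support that. No SD, CV or baseline level is stated, so nothing places the planning SD above or below the 0.59 at which untransformed change drops under 90%. The 50% figure sits at the largest SD that still gives 90% on the log scale. Since the protocol claims more than 90%, the planning SD may have been smaller.

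The simulation is also not the written analysis. It tests a single visit, whereas 9.3.2.2.1 fits a mixed model to six visits. Sidedness is open, and the alternative is directional. Step 5 shows that repeated visits, a one-sided test or a worsening placebo arm would each raise the untransformed figures. These points stand, and they make the power figures illustrations only.

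It can further be said that the text never uses the word untransformed, and that transformation is commonly left to the SAP. This stands only in part. The scale is not merely omitted: the null, E1 and the model are all written as mean change in NT-proBNP. Moving to a ratio of geometric means changes the estimand, and section 9 requires major changes of that kind to appear in an amendment. The mismatch also sits inside 9.5 itself, which sets a relative effect against a null on mean observed change.

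Finally, this is a Phase 1/2 pharmacodynamic endpoint, the misnamed correlation changes no figure, and a log scale is not the only reasonable choice. Analysing percent change gives 93% power at σ = 0.8 in the same simulation. That lowers the urgency but does not remove the inconsistency.

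**Conclusion.** The inconsistency is established from the protocol text. Section 9.5 powers a relative effect, while 9.1.2, E1 and 9.3.2.2.1 define a difference in mean change with no transformation. With no SD, CV, baseline level or sidedness, the power above 90% is unverifiable for the written analysis. It is not shown to be false.

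The possible size depends on assumptions. Under those in step 2, testing untransformed change costs about 11 percentage points of power at a log-SD of 0.6 (99.8 − 89), 33 at 0.8 (95 − 62) and 43 at 1.0 (82 − 39). There is little practical loss below about 0.59. The log scale gave the higher power at every SD compared in the table. The planned 36 participants follow correctly from 15 evaluable per arm and 15% dropout.

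This should be fixed before any unblinded look at the data. It does not by itself invalidate the design.

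**What to change.** Put the primary endpoint on one scale throughout:

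- **9.3.2.2.1:** model change in ln(NT-proBNP).
- **9.1.2 and E1 (synopsis, 3.2, 9.1.3.1):** state the null and the estimand as the Week 24 ratio, PF-07868489 to placebo, of geometric mean fold-change from baseline. Report it with a 95% CI.
- **9.5:** restate on that scale with the target ratio (0.55, if that is what the 45% means), the assumed log-SD and its source, a within-subject correlation of 0.85, the sidedness of the 0.05, and the power that follows.
- **Summaries:** add geometric mean and CV, and keep untransformed summaries as descriptive only.

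The cost is protocol and SAP wording, with no added participants, visits or samples. The small downside is that the effect is reported as a ratio or percent change, not in concentration units. If the log-SD that the sponsor can support is above about 0.89 (two-sided, 15 evaluable per arm, single-visit test), the restated power will fall below 90% unless the repeated-visit model is shown to recover it, and 9.5 should say so.

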9.1.3. Estimands

Estimands defined below are exclusively for Part B. There are no estimands for Part A.

9.1.3.1. Primary Estimand/Coprimary Estimands

E1 (primary analysis estimand): The estimand is the difference between the PF-07868489 and placebo in mean change from baseline in NT-proBNP at Week 24 in PAH patients. This analysis will utilize the Hypothetical approach, excluding data after use of rescue medications prior to week 24 and after study treatment discontinuation.

9.1.3.2. Secondary Estimands

E2 (secondary efficacy estimand): The estimand is the difference between the PF-07868489 and placebo in mean change from baseline in PVR at Week 24 in PAH patients. This analysis will exclude data after use of rescue medications and after study treatment discontinuation.

9.1.4. Multiplicity Adjustment

Not applicable.

9.2. Analysis Sets

For purposes of analysis, the following analysis sets are defined:

Participant Analysis Set	Description
Enrolled	"Enrolled" means a participant's or their legally authorized representative's, agreement to participate in a clinical study following completion of the informed consent process.
PK Population	The PK concentration population is defined as randomized participants who received at least one dose of PF- 07868489 and have at least 1 evaluable concentration. The PK parameter population is defined as all randomized participants who received at least one dose of PF- 07868489 and have at least 1 evaluable PK parameter
PD-Biomarker Population	The PD-Biomarker population is defined as all randomized participants treated who have at least one evaluable NT- proBNP result
PD-Hemodynamic	The PD-Hemodynamic population is defined as all randomized participants treated who have at both PVR measurements (pre- and post-baseline)
Safety analysis set	All participants randomly assigned to study intervention and who take at least 1 dose of study intervention. Participants will be analyzed according to the product they actually received.
Per-protocol Population	All PAH patients in the PD population with no PIPDs. Patients will be analyzed according to randomized treatment assignment.

9.3. Statistical Analyses

The SAP will be developed and finalized before any analyses are performed and will describe the analyses and procedures for accounting for missing, unused, and spurious data. This section is a summary of the planned statistical analyses of the primary and secondary endpoints.

9.3.1. General Considerations

Data will be presented – ie, listed and summarized – by treatment and overall. Continuous data will be summarized comprising mean, median, standard deviation, minimum and maximum. Categorical and binary data are summarized will be done via percentages.

9.3.1.1. Analyses for Longitudinal Continuous Endpoints

Linear mixed models will be used. The fixed effects of treatment, visit, and treatment-byvisit interaction will be included. Visit will be modeled as a categorical covariate. Unstructured covariance matrix will be assumed for the model errors. If the above model does not converge, random intercepts and slopes models with different covariance matrix specifications (eg, compound symmetry) will be tried. Moreover, a visit could be treated as a continuous covariate. Details regarding additional specifications will be described in the SAP.

When modeling the change from baseline values, the variable for visit will start with the first post-baseline visit. At each visit, estimates of least square mean (LSM) values and the LSM differences between treatment groups will be derived from the model. The corresponding p-values and 95% confidence intervals will also be derived from the model.

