Days relative to Day 1	Screen (Up to 35 days before Day 1)	Day 1	Day 8	Day 29	Day 57	Day 85	Day 113	Day 141	Day 169		• Day relative to start of study intervention (Day 1).
			Week 1	Week 4	Week 8	Week 12	Week 16	Week 20	Week 24 / EOT		
Visit Window			±1 day	±2 days	±2 days	±2 days	±2 days	±2 days	±2 Days		 All screening should be done ≤35 days before the first dose. A delay in randomization ≤ 7 days due to the need to acquire RHC, PFT and /or repeat laboratory data will not be considered as a PD. See Section 8.4.3 for follow-up AE and SAE assessments.
Immunogenicity sample collection		Х		Х	Х	X	Х	X	Х	Х	 Samples should be collected pre-dose on dosing days
Target engagement biomarker		Х	X	Х	Х	Х	Х	X	Х	X	Samples should be collected pre-dose on dosing days
NT-proBNP	X	X	Х	Х	Х	Х	Х	X	Х	X	Samples should be collected pre-dose on dosing days
Study Intervention and Other Treatments											See Section 6 for additional information.
Randomization		X		37	37	37		37			
Study intervention administration		X		Х	Х	Х	Х	X			See Section 6.1 for additional information.

Visit Identifier Abbreviations used in this table may be found in Appendix10.							Trea	itment	Period	Early Discontinuation	Notes
Days relative to Day 1	Screen (Up to 35 days before Day 1)	Day 1	Day 8	Day 29	Day 57	Day 85	Day 113	Day 141	Day 169		• Day relative to start of study intervention (Day 1).
			Week 1	Week 4	Week 8	Week 12	Week 16	Week 20	Week 24 / EOT		
Visit Window			±1 day	±2 days	±2 days	±2 days	±2 days	±2 days	±2 Days		 All screening should be done ≤35 days before the first dose. A delay in randomization ≤ 7 days due to the need to acquire RHC, PFT and /or repeat laboratory data will not be considered as a PD. See Section 8.4.3 for follow-up AE and SAE assessments.
Prior/concomitant treatment(s)	X	Х	Х	Х	X	Х	Х	Х	Х	Х	See Section 6.9 For additional information
Assessments											See Section 8 for additional information.
Efficacy											See Section 8.2 for additional information.
6-Minute Walk Test	Х	Х	Х	Х	Х	Х	Х	Х	Х	Х	See section 8.2.2 for additional information.
Borg CR10 scale® (pre- and post-6MWT)	X	Х	Х	X	X	X	X	X	Х	X	To be completed before and after each 6MWT. See Section 8.2.4.6. for additional information.
WHO Functional Class Assessment	Х	Х	Х	Х	X	Х	Х	Х	Х	Х	See Section 8.2.3 for additional information
Patient Reported Outcome Measures											See Section 8.2.4 for additional information.

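### The primary NT-proBNP model omits baseline NT-proBNP from its listed fixed effects, although the value is collected; adding it costs little and gains modestly on the log scale, more on the raw scale

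*Protocol*

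**What the plan says.** Section 9.3.1.1 gives the general model for longitudinal continuous endpoints: "The fixed effects of treatment, visit, and treatment-byvisit interaction will be included". It then adds: "Details regarding additional specifications will be described in the SAP".

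Section 9.3.2.2.1 gives the primary analysis: "Change from baseline relative to placebo will be analyzed using a linear mixed model". The model uses six visits and two named fixed effects: "linear mixed model including data from Weeks 4, 8, 12, 16, 20 and 24 with treatment and time and fixed effect (Section 9.3.1". The random part covers participant, time or both. Baseline NT-proBNP appears in neither list.

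The data exist. The NT-proBNP row of Table 3 (Section 1.4.1.1) is marked at Screening and at Day 1, with the note "Samples should be collected pre-dose on dosing days".

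Section 9.5 sizes Part B as "a total of 36 PAH patients randomized 1:1 to either PF-07868489 or placebo", aiming for 15 evaluable per arm and power above 90%. Its premises are stated as "Assuming an inter-subject correlation of 0.85, 15% of patients drop out for non-study reasons and a type 1 error rate of .05". Sections 4.1.2 and 6.3.2 describe 1:1 allocation through the IRT and name no stratification factor.

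**The concern.** A change score fixes the coefficient of baseline at 1. Unless the true slope is 1, part of the baseline value stays in the change as noise, and a chance baseline difference between arms leaks into the treatment contrast through regression to the mean. A baseline covariate estimates the slope and removes both effects.

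In a trial of 36 with NT-proBNP as the primary efficacy endpoint, precision is scarce, and here it can be had from samples already planned. The protocol is also not silent: it names the fixed effects, and baseline is not among them. Section 9 says that major modifications of the primary analyses will also be reflected in a protocol amendment, so the covariate is best settled in both documents before unblinding.

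**Working it through.** **Inputs from Section 9.5:** correlation 0.85, dropout 15%, alpha 0.05, 36 randomised, 15 evaluable per arm, a 45% greater decline than placebo.

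**Assumptions, because the protocol does not state them:**
- The correlation, worded there as inter-subject, is read as the within-participant correlation r between baseline and Week 24.
- The effect is a ratio of 0.55, so the log difference is |ln 0.55| = 0.598.
- Tests are two-sided.
- Variance σ² is equal at baseline and Week 24.
- The Week 24 contrast is treated as a two-group comparison. The random-slope form could move the figures somewhat.

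**Step 1. The plan's own figures.** 30/(1 − 0.15) = 35.3, rounded up to 36, and 36 × 0.85 = 30.6. The sample size reproduces. The power does not follow from the text, because no SD is given. With 15 per arm, a two-sided t-test reaches 90% when the SD of the log change is at most 0.487. As SD(change) = σ√(2(1 − r)) = 0.548σ, this means a log-SD σ of at most 0.89.

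**Step 2. Covariate alone, large sample.** In units of σ²:
- Change score: 2(1 − r) = 0.300.
- Baseline-adjusted: 1 − r² = 0.2775.
- Ratio: (1 + r)/2 = 0.925, a cut of 7.5%.

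**Step 3. Cost of estimating the slope with 15 per arm.** The factor is about 1 + 1/26 = 1.038, and 0.925 × 1.038 = 0.961. The net cut is about 4% (standard error down 2.0%). Simulation of 40,000 trials per correlation agrees. In the table, σ is set so that the unadjusted t-test has 90% power.

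| r | Asymptotic ratio | Net ratio, formula | Net ratio, simulated | Power, unadjusted to adjusted |
|---|---|---|---|---|
| 0.85 | 0.925 | 0.961 | 0.961 | 90% to 91% |
| 0.70 | 0.850 | 0.883 | 0.888 | 90% to 93% |
| 0.50 | 0.750 | 0.779 | 0.781 | 90% to 96% |

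**Step 4. Untransformed scale.** Sections 9.1.2, 9.1.3.1 and 9.3.2.2.1 speak of mean change and name no log transformation. I simulated lognormal values with log-SD 0.89, r = 0.85, a Week 24 ratio of 0.55 and no placebo change. The covariate cuts the variance of the contrast by about 46%, and power goes from about 51% to about 71%. At log-SD 1.0 the cut is about 51% to 52%, and power goes from about 38% to about 56%. One caveat: with a proportional effect a common raw-scale slope is only approximate. At log-SD 0.89 the adjusted estimate averaged −0.63, against −0.67 unadjusted (in units of the median baseline).

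**Step 5. Averaging two pre-dose values, a separate change.** If Screening and Day 1 correlate q, their mean has variance (1 + q)/2, and the change score without any covariate has variance 1 + (1 + q)/2 − 2r, with r = 0.85.
- q = 0.85: 1 + 0.925 − 1.70 = 0.225, a 25% cut from 0.300. The covariate then gives 1 − 0.7225/0.925 = 0.219, a further 2.7%.
- q = 0.95: 1 + 0.975 − 1.70 = 0.275, an 8% cut. With the covariate, 1 − 0.7225/0.975 = 0.259, a total asymptotic cut of 13.7%.

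The documents give no value for q.

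**Step 6. Chance imbalance.** The arm difference in mean baseline has SD √(2/15) = 0.365σ. The probability that it exceeds 0.5σ in either direction is that of |Z| > 0.5/0.365 = 1.37, about 17%; above 0.75σ it is about 4%. A share of 1 − r carries into the unadjusted change contrast. At r = 0.85 that is 15%, so a 0.5σ imbalance with σ = 0.89 shifts the estimate by 0.15 × 0.5 × 0.89 = 0.067, against an effect of 0.598.

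**The case against.** The best defence is that covariates are ordinary SAP content. Section 9.3.1.1 sends additional specifications to the SAP, Section 9.3 calls itself a summary, and nothing excludes a baseline term. That stands as a limit. A reader might infer that the protocol rules out baseline adjustment; it does not. What remains is that it chose to list the primary model's fixed effects, and the list is less efficient than it need be.

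The second defence is size: at the stated correlation, on the log scale, the covariate is worth about one point of power. That also stands.

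Three stronger readings are tempting and not supported:
- **The omitted covariate costs about 27% of variance.** That total at r = 0.85 is nearly all from averaging two pre-dose samples. It also requires samples taken within the 35-day Screening window to correlate no better than baseline and Week 24 do.
- **Nothing handles baseline imbalance, and a large one is likely.** The change score already removes 85% of an imbalance at r = 0.85, and one above 0.5 SD has about a 17% chance. Under randomisation the unadjusted contrast is unbiased on average; the bias is conditional on the imbalance observed.
- **The same covariate is missing for PVR.** Section 9.3.3.1.1 models observed PVR with the pre-baseline value among the responses. Adding it as a covariate would put the same value on both sides.

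**Conclusion.** The point holds as an efficiency improvement to a stated model. It does not make the planned analysis invalid. Both fixed-effect lists omit a baseline value that the trial collects.

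On the log scale at r = 0.85 the loss is small, about 4% to 5% of variance net. It becomes material if the true correlation is nearer 0.7 or 0.5, and large if NT-proBNP is analysed untransformed. These sizes rest on reading 0.85 as the baseline-to-Week 24 correlation, on assumed log-SDs, and on an effect ratio of 0.55. The direction on the log scale needs only equal variances and r below 1, by enough to repay the small cost of estimating the slope: that cost uses up the gain only when r is above about 0.92, since (1 + r)/2 × 1.038 = 1 there.

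The SAP was not available for this check. If it already includes the covariate, only alignment of the protocol text remains.

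**What to change.** In Sections 9.3.1.1 and 9.3.2.2.1, add baseline NT-proBNP and baseline-by-visit to the fixed effects of the primary model, with baseline on the same scale as the response (log baseline if the response is log change). Use the same specification in the SAP. Apply the same covariate to 6MWD if it is analysed as change from baseline, and leave the PVR model as it is on this point.

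Optionally, define baseline as the mean of the Screening and Day 1 pre-dose values, averaged on the analysis scale. Justify this separately, because its gain depends on a correlation that the protocol does not give.

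The cost is a few lines of text and, with visit categorical over six visits, up to six fixed-effect parameters (one baseline term and five interactions). No new samples or visits are needed.
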